4.5. Electrocardiogram

A 12-lead electrocardiogram (ECG) will be performed during the Screening Period to document clinically significant anomalies (if not done up to 6 months prior to Day 0).

4.6. Angiogram

An aorto-iliac angiogram will be performed and will be used to determine the suitability of the subject for enrollment into the study and to determine injection site locations. The angiogram may have been completed up to 3 months prior to the start of screening, as long as the subject's clinical condition has not changed since the angiogram was performed or undergone a bypass or endovascular intervention within the previous 3 months. Acceptable forms of imaging for this trial also include Computerized Tomography Angiogram (CTA) and Magnetic Resonance Angiogram (MRA). An angiogram will also be required to be performed prior to a proposed surgical revascularization or major amputation.

4.7. Peripheral Vascular Intervention History (or Update)

During Screening

At Screening, the Investigator will perform a detailed assessment of all past peripheral vascular interventions (surgical bypass, an endovascular intervention or major/minor amputations). If the subject has never undergone a peripheral vascular intervention then the lack of these events will be documented as well. Information may include: date(s) of intervention, type(s) of intervention (e.g., PTA, surgical bypass, amputation, etc.), intervention site (e.g., iliac, femoro-popliteal, infrapopliteal, etc.), intervention side (right or left leg and index or non-index leg) conduit used (e.g., saphenous vein, polytetrafluoroethylene [PTFE], human umbilical vein [HUV], Dacron, etc.), and patency of most recent intervention prior to study start (including a description of the results from the most recent vascular imaging if available). Information concerning both major (defined as at or above the ankle) and minor (below the ankle) amputation should be collected. Specific information for each peripheral vascular procedure will be obtained and recorded on the

subjects' source documentation and CRF to allow independent review of the subjects' CLI status and suitability for entry into the study.

During Treatment and Follow up Period

During the study, detailed information must be documented in the subjects' source documentation and CRF on the subject's CLI status of the index leg including any treatment received for worsening CLI of the index leg, plan for major or minor amputations of the index leg, plan for revascularization procedures of the index leg, etc. Detailed information on the subjects' CLI status must be documented prior to planning a surgical revascularization or major amputation of the index leg. Data relating to the reasons for performing a surgical revascularization or major amputation of the index leg will be reviewed.

In no way will intervention that is deemed necessary be withheld for any subject.

4.8. Hemodynamic Measurements

The hemodynamic status of the affected lower limb will be evaluated to confirm the CLI diagnosis, and the subject's suitability for inclusion into the study. The ankle and toe pressures will be measured using Doppler or a photoplethysmograph (PPG) and the ankle/brachial index (ABI) and toe/ brachial index (TBI) will be estimated in the index leg, measuring both the posterior tibial and dorsalis pedis arteries for the ABI. The higher of the two readings will be used. The methodology for obtaining these measurements is outlined in Appendix B. A Vascular Report must be included in the source documentation to support the hemodynamic data.

During Screening hemodynamic measurements are required for both the index and non-index leg. Otherwise, at all other time points during the study, hemodynamic measurements are only required for the index leg.

If it is not possible to obtain the toe pressure because the big toe has been amputated, or is too deformed or necrotic to apply the cuff, then the second toe may be used. This should be noted in the source documentation and in the CRF.

A vessel with no detectable Doppler signal (complete occlusion) will be recorded as having a zero pressure ("0 mmHg"). Calcification of the media is common in diabetic subjects, rendering the tibial and peroneal arteries non-compressible, which causes falsely elevated ABI (>1.30). If the measurement cannot be assessed due to calcification then the non-compressible status of these arteries should be noted in the source documentation and CRF and the toe pressure used to diagnose and assess CLI.

4.9. Assessment of CLI and Ulcer Photography and Tracings

For study entry, the subject must be evaluated for clinical evidence of CLI according to the definition of the study population for this protocol found in Section 3.1 Study Population.

The Investigator must assign a baseline status to the subject's peripheral vascular disease based on the status of the index leg using the Rutherford Classifications (see Appendix C). In case of Rutherford Category 4 and Rutherford Category 5, the Principal Investigator must make sure that the inclusion criteria for subjects with Rutherford Category 4 and Rutherford Category 5 are

strictly followed for the subjects to be eligible to enter the study. (See Section 3.1 Study Population)

During the study, specific information on the subject's CLI status will be documented on the CRF and in the source documentation including information on ulcers/gangrene, rest pain, debridement/wound care, infection treatment, hospitalizations, minor and major amputations, revascularization by surgical bypass, etc.

In order to accurately assess ulcer size, the ulcer (s) must be cleaned and debrided to remove necrotic tissue, eschar, and callouses prior to photographs and ulcer tracings, as per the wound care guidelines (see Appendix D).

During Screening, ulcer photography and tracings of the largest ulcer (with ulcer debridement occurring prior to photography and tracing) must be performed and used as one of the evaluations to be made to confirm CLI stability for entry into the study. Ulcer photography at screening should include one photograph of the largest ulcer on the index leg and additional photographs of the index leg that capture the foot and lower leg to confirm the location of the largest ulcer, as well as all additional ulcers (and gangrene) and the overall status of the index leg at screening.

Prior to dosing on Day 0, ulcer photography and tracing of the largest ulcer as at Screening (with ulcer debridement occurring prior to photography and tracing) will be completed again for establishing stability of the largest ulcer and of additional ulcers on the index leg prior to randomization. Ulcer photographs and photographs of the index leg will be taken at each visit (Day 14 through Month 18) and prior to any planned intervention of the index leg (surgical revascularization or major amputation). If the largest ulcer on the index leg heals during the study period, the ulcer must be re-evaluated 2 weeks after healing to confirm it has remained healed for a period of 2 weeks (this will require an additional visit to the site). Ulcer healing will be confirmed later via photographs by the study entry committee. *Ulcer and leg photographs must continue to be taken throughout the study period, regardless of the healing of the largest ulcer.*

4.10. Laboratory Tests

The following clinical laboratory tests will be performed:

1. Hematology: including hemoglobin, hematocrit, RBC count, WBC count (total and differential) and platelet count.
2. Urinalysis including protein, glucose, blood, ketones, bile, and microscopic examination.
3. Blood chemistry: glucose (fasting), uric acid, total cholesterol, HDL, calculated LDL, triglycerides, aspartate transaminase (AST), alanine aminotransferase (ALT), calcium, phosphorus, total bilirubin, alkaline phosphatase, total protein, albumin, globulin, lactic acid dehydrogenase (LDH), serum creatinine, creatinine clearance (estimated using the Cockroft Gault formula), blood urea nitrogen (BUN), and electrolytes (Na⁺, K⁺, Cl⁻)).
4. Serum HGF protein assay and PCR for HGF plasmid and Anti HGF antibodies
5. HbA1c in diabetic subjects

6. FSH and estradiol levels in women 55 years or less (screening only)
7. Urine Pregnancy Test (screening only)

See Section 5 for screening period procedures, Table 3 “Schedule of Study Procedures” and Table 4 “Schedule of Sample Collection for the Serum HGF protein & PCR for HGF Plasmid Assays” for details on what visits these laboratory samples should be collected. Please see the Laboratory Procedure Manual for details regarding blood drawing, storage, processing, and transport.

Diabetic status: To determine the subjects’ diabetic status at screening, all subjects will have their fasting blood glucose (FBG) measured. In subjects with known diabetes, supportive documentation will be required to confirm the diagnosis, e.g., evidence of raised blood glucose levels, treatment with insulin or oral anti-diabetic drugs. Diagnostic criteria for diabetes are in the table below.

Diabetic Status Criteria

If FBG < 7.0 mmol/L (126 mg/dL)	Non-diabetic
If FBG ≥ 7.0 mmol/L (126 mg/dL), or previous diabetes diagnosis	Diabetic

4.11. Ischemic Rest Pain Measurement

The severity of rest pain based on the average over the previous 7 days will be recorded using the 10 cm visual analog scale (VAS) (see Appendix E). The VAS score must be documented at all visits and prior to any planned intervention (revascularization or major amputation). In order to assess rest pain adequately, the use of pain medication/opioids must be specifically documented in the CRF during the VAS evaluation period. The subject should not be allowed to see his previous rest pain measurements nor should the score be revealed to him/her.

4.12. Post-Dosing Procedures

Blood samples will be obtained for measurement of serum HGF protein and HGF plasmid DNA four (4) hours after the injections are completed. These blood samples are required at certain dosing visits as per Table 4 “Schedule of Sample Collection for the Serum HGF protein & PCR for HGF Plasmid Assays”.

All subjects should be observed and Adverse Events (AEs) recorded. Subject will be discharged from the clinic when clinically stable.

4.13. Adverse Event Review

The Investigator should start documenting adverse events after the first dose of study product administration, during study product administration, post treatment and throughout the study period (Month 18 Visit). See Section 8.0 Adverse Events for details.

Events relating to the worsening of CLI that occur in the index limb such as increased rest pain, new ischemic ulceration or increase the size of the ulcer, gangrene, cellulitis or osteomyelitis, and redness that are related to the study disease and are symptoms/signs of progression of study disease will not be recorded as adverse events (unless the speed or extent of the symptoms/signs are unexpected based on the natural history or bear a strong temporal relationship to the study product). Data on the subject's CLI status of the index limb will be recorded in detail on non-AE CRFs and is therefore not required to be documented as an AE or SAE.

In cases which any of the worsening of CLI events that occur in the index limb such as increased rest pain, new ischemic ulceration or increase in the size of the ulcer, gangrene, cellulitis or osteomyelitis, and redness that are symptoms/signs of progression of critical limb ischemia, **and that result in death**, the event should be reported as an SAE.

Systemic or metabolic complications that ensue subsequent to worsening CLI of the index leg should be reported as AEs or SAEs. Systemic complications include events such as septicemia, pneumonia, multi-organ failure and events resulting in death. These events should be captured on the AE or SAE section of the CRF. Metabolic complications include excessive increase in blood glucose or serum creatinine. Events that result in death should be reported as a SAE.

Limb specific events that occur in the **non-index limb** such as increased ischemic rest pain, new ischemic ulceration or increase in the size of the ulcer, gangrene, minor or major amputations, will be recorded as an AE or SAE on the AE CRF.

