8.1.1. Adverse Events Associated with Worsening CLI

Adverse Events relating to the worsening of CLI that occur in the index limb such as increased rest pain, new ischemic ulceration or increase the size of the ulcer, gangrene, cellulitis or osteomyelitis, that are related to the study disease and are symptoms/signs of progression of study disease will not be recorded as adverse events (unless the speed or extent of the symptoms/signs are unexpected based on the natural history or bear a strong temporal relationship to the study product as determined by the Investigator). Data on the subject's CLI status of the index limb will be recorded in detail on non-AE CRFs and not required to be documented as an AE or SAE, unless the outcome of the event is death.

Systemic or metabolic complications (e.g., diabetic ketoacidosis, renal failure, etc.) that ensue subsequent to worsening CLI of the index leg should be reported as AEs or SAEs. SAEs due to systemic complications include events such as septicemia, pneumonia, multi-organ failure and events resulting in death. These events should be reported as an SAE.

Limb specific events that occur in the **non-index limb** such as increased rest pain, new ischemic ulceration or increase in the size of the ulcer, gangrene, minor or major amputations, will be recorded as an AE or SAE on the AE CRF

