9. EVALUATIONS AND STATISTICAL METHODS

9.1. Evaluations

The following evaluations relating to tolerability, safety and clinical benefit will be made:

1. Adverse events (AEs) suspected to be related to injections of HGF plasmid
2. Discontinuations related to adverse effects from the injections of HGF plasmid
3. All AEs up to Month 3, Month 6, Month 12, and Month 18
4. Serious adverse events (SAEs) up to Month 3, Month 6, Month 12, and Month 18
5. Number of deaths and cause over the 18 month period up to Month 3, Month 6, Month 12, and Month 18
6. Number of subjects in whom the largest ulcer healed completely or gets smaller (photo confirmation) at 6, 12 and 18 months (cumulative)
7. Number of subjects in whom rest pain (based on the 100 mm VAS scale) reduces by 20 mm or more or was completely relieved at 6, 12 and 18 months (cumulative)
8. Change in VascuQol Questionnaire (QOL) score compared to the baseline at 6, 12 and 18 months
9. Number of subjects revascularized (bypass or endovascular intervention) up to Month 3, Month 6, Month 12, and Month 18
10. Number of subjects with minor and number of subjects with major amputations (at or above the ankle) up to Month 3, Month 6, Month 12, and Month 18

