2.5.5 Efficacy Analysis

- Ulcer improvement**

A table showing the number of subjects completely healed in the target ulcer will be provided at up to 6 months, > 6 months to 12 months, from >12 months to 18 months. If available, the number of subjects with at least 20% reduction in bi-dimensional size (by measuring largest diameters) will be provided. The reduction in bi-dimensional size will be calculated by taking the product of the largest diameters for each baseline and postbaseline measurement, then subtracting the baseline result from the postbaseline result.

- Ischemic Rest pain (of the index leg) using a 10 cm VAS scale**

Rest pain severity will be assessed at the specified predetermined time points. Rest pain severity will also be assessed prior to surgical revascularization or major amputation (of the index leg). A table showing the number of subjects reduced by ≥ 20 mm from baseline in VAS score will be provided at up to 6 months, > 6 months to 12 months, from >12 months to 18 months. Summary statistics will be provided for baseline and change from baseline for each visit and LOCF. One sample t-test for change-from-baseline will be performed. If death occurs, the worst score prior to death instead of last observation will be carried forward.

- Hemodynamic Measurements**

Summary statistics will be provided for baseline and change from baseline for hemodynamic parameters (right/left brachial systolic pressure, ankle systolic pressure measured at dorsalis pedis and posterior tibial, toe systolic pressure, calculated ABI, and calculated TBI) by visit. At each visit, only subjects who have a non-missing value at both baseline and the specific visit will be summarized. Two-sided one-sample t-test will be performed for each visit and LOCF.

- Subjects with any worsening CLI event of index leg**

A summary table and listing of worsening CLI-related events of the index leg including any new or worsening events, worsening rest pain, new ulcer or worsening ulcer, new or worsening wound infection, peripheral vascular intervention, complication of a peripheral vascular intervention, cellulitis, and amputation due to worsening CLI will be provided.

- Subjects who either died, had MI, Stroke, revascularization (by surgical bypass, by endovascular intervention, by hybrid procedure), major amputation, or all-cause death**

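### Local tolerability may be understated: index-limb cellulitis or redness attributed to CLI progression stays off the AE form, although every injection goes into that limb

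*Protocol*

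**What the plan says.** - **Rule.** Protocol 4.13 covers index-limb signs of worsening CLI and keeps them off the AE form: "cellulitis or osteomyelitis, and redness that are related to the study disease and are symptoms/signs of progression of study disease will not be recorded".
- **Exception.** The same sentence restores AE recording when speed or extent is unexpected for the natural history, or when the signs "bear a strong temporal relationship to the study product". Protocol 8.1.1 has the exception as "bear a strong temporal relationship to the study product as determined by the Investigator", and 8.1.2 assigns the decision in the same way for serious events. No section gives a number of days or a location rule.
- **Where excluded events go.** "Data on the subject's CLI status of the index limb will be recorded in detail on non-AE CRFs" (4.13). Deaths and systemic complications are still reported as AEs or SAEs.
- **Parallel list.** Protocol 8.1.1 names "gangrene, cellulitis or osteomyelitis, that are related to the study disease"; redness is absent there and in 8.1.2.
- **Injection site.** Protocol 3.4 sends all eight injections at each dosing visit into the index leg.
- **Objective and evaluation.** Tolerability of the modified regimen and safety are the primary objectives (Protocol 2, SAP 2.1). The first evaluation in Protocol 9.1 is "Adverse events (AEs) suspected to be related to injections of HGF plasmid".
- **Analysis.** SAP 2.5.7 builds its AE tables from the standard AE form. SAP 2.5.5, under efficacy, plans a worsening-CLI table and listing for the index leg. Its named items end with "new or worsening wound infection, peripheral vascular intervention, complication of a peripheral vascular intervention, cellulitis, and amputation due to worsening CLI will be provided".

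**The concern.** The limb that receives the product is also the limb for which the AE rule has a carve-out. The uninjected leg has none: Protocol 4.13 and 8.1.1 record limb events in the non-index leg as AEs. In the injected leg, whether redness or cellulitis counts as an AE depends on one judgement about its cause. SAP 2.2 describes an open-label, single-centre study, so the investigator who makes that judgement knows that product was given.

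The carve-out can only take events out of the AE count, and no control arm would reveal a shift. No independent check of this attribution is described: the entry committee's listed tasks (Protocol 5, after Table 2) include adjudicating revascularization and major amputation, but not the cause of redness or cellulitis. What is at stake is how far the AE tables can be relied on for local tolerability.

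**Working it through.** The documents state no event rate, power or target for local reactions, so there is no planned figure to reproduce. The check compares the texts and then sets the scale.

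**1. What each section names**

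| Place | Cellulitis | Osteomyelitis | Redness | Destination |
|---|---|---|---|---|
| Protocol 4.13 | yes | yes | yes | non-AE forms |
| Protocol 8.1.1 | yes | yes | no | non-AE forms |
| Protocol 8.1.2 (serious) | yes | yes | no | CLI section of the CRF |
| SAP 2.5.5 | yes | no | no | worsening-CLI table, efficacy |

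An event judged to be progression goes to the CLI forms. SAP 2.5.7 takes AEs from the AE form, so that event cannot reach the table of related AEs. If it is tabulated, that happens in 2.5.5, which does not split by dosing course or by time since injection. No planned table joins the two sources.

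**2. Exposure of the limb** (Table 1 and Protocol 3.4)

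4 courses × 4 dosing visits = 16 visits; 16 × 8 = 128 injections per fully dosed subject, all in the index leg.

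**3. How open the timing exception is**

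Follow-up to Month 18 is 18 × 30 = 540 days. Courses start on days 0, 90, 270 and 360, with sets 14 days apart. Counting the injection day as the first day, windows of up to 14 days do not overlap. The documents set no window, so these three are assumptions:

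- 3 days: 16 × 3 = 48; 48/540 = 9%
- 7 days: 16 × 7 = 112; 112/540 = 21%
- 14 days: 16 × 14 = 224; 224/540 = 41%

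These are shares of calendar time, not of events. They show only that the exception can be read narrowly or widely.

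**4. Weight of one subject** (n = 8 to 10, Protocol 3)

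Take one subject whose only local reaction is put down to CLI. Intervals are exact (Clopper-Pearson) 95%.

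- n = 10: 1/10 = 10.0% (0.3% to 44.5%) becomes 0/10 (0% to 30.8%), a change of 10.0 points.
- n = 8: 1/8 = 12.5% (0.3% to 52.7%) becomes 0/8 (0% to 36.9%), a change of 12.5 points.

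**5. Illustration under assumed rates**

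Let p be a subject's risk of a local reaction and m the fraction routed to the CLI form. The chance of seeing at least one as an AE is 1 − (1 − p(1 − m))^n. Neither p nor m is in the documents. For n = 10:

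| p | m = 0 | m = 0.25 | m = 0.5 | m = 0.75 |
|---|---|---|---|---|
| 10% | 65% | 54% | 40% | 22% |
| 20% | 89% | 80% | 65% | 40% |
| 30% | 97% | 92% | 80% | 54% |

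At m = 0 nothing is lost.

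**The case against.** The case on the other side is substantial.

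- **The exception is aimed at this problem.** The exclusion reaches only events judged both related to CLI and a sign of its progression, and it gives way when timing points to the product. A sign close to dosing may thus be more likely to be recorded as an AE. This stands, but the criterion has no window and the investigator applies it.
- **Injection-related AEs are asked for elsewhere.** Protocol 4.12, 5.3.3, 5.6.2 and 5.9 require AEs to be recorded during or after injection, and 5.5 treats a hematoma as an AE. This stands for events recognised as reactions; it does not settle ambiguous ones.
- **Location evidence exists.** Appendix A advises against injecting ischemic areas, sites are marked and photographed at each dose, and the leg is photographed at each visit (4.9). The AE text does not call on this evidence, dosing-day site photographs precede any delayed reaction, and the SAP plans no analysis of them.
- **Excluded events are not lost.** The worsening-CLI table has an open category for any new or worsening event. SAP 2.5.7 also counts physical-examination abnormalities by dosing block, whatever their cause. Both points stand. However, the first would not make redness identifiable, and the second rests partly on abbreviated, symptom-driven examinations (Protocol 4.3).
- **The lists are illustrative.** Both 4.13 and 8.1.1 give examples, so the difference over redness is one of wording, and deleting the word would change little. This stands.

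A reader might infer that all index-limb redness and cellulitis is excluded, that tolerability is in fact understated, or that 41% of events are affected. The documents support none of these. The rule is conditional, no misrouting rate is given, and 41% is calendar time under a window that the plan does not set. Nor do the documents give frequencies for local reactions, so nothing can be said about which are commonest.

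**Conclusion.** The concern holds as a risk of under-ascertainment. For index-limb signs that could be either a local reaction or CLI progression, entry into the AE tables depends on an open-label investigator's attribution under a timing criterion with no window, and the SAP has no analysis free of that attribution. Local tolerability may therefore be understated. The amount is unknown and could be zero.

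The firm figure is the weight of one subject, 10 to 12.5 points with 10 or 8 subjects, given that this subject has no other local AE. The detection probabilities rest on assumed rates and serve as illustration only. The study is a descriptive pilot with line listings, so no formal inference is at risk; what is affected is how a low count of local AEs can be read.

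**What to change.** **SAP 2.5.7.** Add a table and a listing of all index-limb local events: redness where recorded, cellulitis, wound infection, osteomyelitis and gangrene. Pool the AE form and the non-AE CLI forms, count events regardless of attribution, and show the source form. Present the table by dosing course and by days since the last injection (under 14 against 14 or more), with the actual number of days in the listing so that a reader can apply another window. For a fully dosed subject the planned split is 224 days against 540 − 224 = 316 days, so the counts should be read against the time in each category.

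**Protocol 4.13, 8.1.1 and 8.1.2.** Reconcile the wording on redness so that sites read one rule. This is for consistency; it does not remove the dependence on attribution, which the SAP table addresses.

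**Cost.** One extra table with its listing, built from events that the protocol already sends to the AE or CLI forms. The reported rate of local events may rise and will include true CLI progression, so a footnote should say so. The CLI forms are not among the documents, so onset timing, and whether redness is identifiable at all, are limited to what those forms record.
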